1 PROTOCOL SUMMARY**1.1 SYNOPSIS**

Title: **Automated Reinforcement Management System (ARMS)**

Grant Number: R41 AA0267993

Study Description:

Alcohol abuse remains a significant cause of preventable morbidity and mortality in the US, yet only 15% of those with alcohol use disorders receive treatment. Contingency Management (CM) is a cost-effective intervention for drug addiction where individuals are rewarded when they submit biological verification of drug abstinence. We propose to develop an integrated CM system capable of incorporating mobile device input and Electronic Medical Record (EMR) integration, that would allow us to deliver a CM intervention for problematic drinking to anyone who owns a smartphone. The mobile device input will incorporate ecological momentary assessments (EMA), geospatial mapping, and biomarker-based feedback from a portable measuring device. This novel approach will enable personalized CM goal setting and a new platform for clinician feedback and progress monitoring. The goal of the system will be to provide an end-to-end CM platform, which can aggregate and inform the understanding of mechanisms underlying the initiation, maintenance, and recovery from problematic drinking in both treatment and naturalistic settings with little to no required clinician involvement.

Objectives*:

Primary Objective: To develop and combine mobile technology, geospatial mapping, and biomarker measurement, with individual goal setting and EMA feedback to launch behavioral modification strategies and progress monitoring.

Secondary Objectives: To develop and consumer-test the mobile application component to help the patient alcohol-related treatment goals at home.

Endpoints*:

Primary Endpoint: Our primary endpoint is biochemically confirmed alcohol abstinence, measured thrice daily throughout the 8-week study.

Secondary Endpoints: Secondary endpoints will include self-reported alcohol use measured by the Timeline Follow Back to assess the frequency and amount of daily drinking via multi-modal EMA data collection.

Study Population:

Twenty (20) subjects, male and female, between 18 and 65 years of age who have an Alcohol Use Disorders Identification Test (AUDIT) score of eight or higher. Subjects must read and speak English and have the ability to provide written informed consent. They must also live in the Greater Inland Northwest area (i.e., Spokane and Coeur d'Alene).

Phase* or Stage:

Phase I, Clinical Analog Trial with A-B-A phase design.

**Description of
Sites/Facilities Enrolling
Participants:**

This study will take place in Greater Inland Northwest area in cooperation with the Community Health Association of Spokane (CHAS) and other clinical referral entities throughout the Spokane region, including MultiCare Health System (MHS) and others.

Description of Study

Intervention/Experimental Manipulation: We will utilize an A-B-A, completely within-subject design with the intent of recruiting twenty (n=20) total participants.

During the first A phase, participants will receive reinforcement for simply submitting breath samples three times per day between 4 and 6 hours apart. In this application, we will use a Bluetooth enabled breathalyzer developed by BACtrack, however our smartphone-based technological solution will interact with any alcohol monitoring device, such as BACtrack Skyn.

During the B phase, the delivery of reinforcers will be contingent upon the submission of an alcohol negative breath sample on an escalating schedule.

The A phase or return to the baseline phase will involve the delivery of reinforcers for simply submitting a breath sample during the designated windows of time. We will also collect EMA data on stress, anxiety, depression, and other brief measures daily through their smartphone.

Each phase will last a total of four weeks (i.e., two weeks of the first A phase, four weeks of the B phase, and then two more weeks of the A-phase) each for a total of 8 weeks of participation. To the extent possible, we will use existing protocols, procedures, and equipment that we have used in previous A-B-A studies.

Study Duration*: Eight to twelve months.

Participant Duration: Two months for each participant to complete all study-related tasks.

1.2 SCHEDULE OF ACTIVITIES

Table 1. Schedule of study activities.

| | Baseline Week 0 | A-B-A Week 1-8 |
|--------------------------------------------------------------------|----------------------------|---------------------------|
| Informed consent | ✓ | |
| M.I.N.I*. Research Psychiatric Diagnosis | ✓ | |
| Medical history form | ✓ | |
| Other inclusion/exclusion criteria | ✓ | |
| Alcohol use (biochemical BAC **) | ✓ | 3x / day |
| Alcohol Timeline Follow Back (self-report) | ✓ | 3x / day |
| Addiction severity Index: ASI-Lite (self-report) | ✓ | |
| Alcohol cravings and withdrawal: visual analog scale (self-report) | ✓ | 3x / day |
| Location and Activity at time of the report | ✓ | 3x / day |
| Other substance use (biochemical) | ✓ | |
| Health-related quality of life (self-report) | ✓ | |
| Tobacco dependence (Fagerström***) | ✓ | |
| Alcohol dependence (AUDIT****) | ✓ | |
| Adverse Events | ✓ | weekly |
| Psychopathology (BSI*****) | ✓ | |
| Follow-up phone call | ✓ | weekly |
| Sleepiness Scale | ✓ | Weekly |

*The Mini-International Neuropsychiatric Interview (**M.I.N.I.**) is a short structured diagnostic interview, developed jointly by psychiatrists and clinicians.

**Blood Alcohol Concentration (BAC).

***The Fagerström Test for Nicotine Dependence is a standard instrument for assessing the intensity of physical addiction to nicotine.

****The Alcohol Use Disorders Identification Test (AUDIT).

*****The Brief Symptom Inventory (BSI).

2 INTRODUCTION

2.1 STUDY RATIONALE

Alcohol abuse remains a significant cause of preventable morbidity and mortality in the US, yet only 15% of those with alcohol use disorders receive treatment. Contingency Management (CM) is a cost-effective intervention for drug addiction where individuals are rewarded when they submit biological verification of drug abstinence.¹⁻⁷ We propose to develop an integrated CM system capable of incorporating mobile device input and Electronic Medical Record (EMR) integration, that would allow us to deliver a CM intervention for problematic drinking to anyone who owns a smartphone. The mobile device input will incorporate ecological momentary assessments (EMA), geospatial mapping, and biomarker-based feedback from a portable measuring device. This novel approach will enable personalized CM goal setting and a new platform for clinician feedback and progress monitoring. The goal of the system will be to provide an end-to-end CM platform, which can aggregate and inform the understanding of mechanisms underlying the initiation, maintenance, and recovery from problematic drinking in both treatment and naturalistic settings with little to no required clinician involvement.

2.2 BACKGROUND

In a recently completed randomized controlled trial (RCT; n=79) we used ethyl glucuronide (EtG), a urine-based biomarker capable of detecting heavy drinking for up to five days, as the basis for a CM intervention for alcohol use disorders in outpatients who suffered from comorbid mental illness (PI: [name], Co-I: [name]; Am J Psychiatry). We found that participants randomized to CM were 3.13 times more likely than controls CI=2.18-4.50, p<0.01) to submit alcohol-negative urine samples during the 12-week treatment period. They also achieved longer duration of alcohol abstinence: 2.9 weeks (SD=3.30) versus 1.4 weeks in the control group (SD=2.10; p<.02). The CM group also had significantly:

- 1) lower average EtG levels,
- 2) fewer days of any drinking or heavy drinking during treatment, and
- 3) fewer days of drinking during the 6-month follow-up.

These results provide convincing evidence for the efficacy of CM in treating people who have an alcohol use disorder.

2.3 RISK/BENEFIT ASSESSMENT

2.3.1 KNOWN POTENTIAL RISKS

The risk to patients from digital intervention is negligible. However, as in all trials of this nature, there is the possibility of unauthorized disclosure of confidential information; discomfort, or embarrassment related to biologic sample collection or administration of questionnaires or assessments dealing with sensitive information. There may be unforeseen and unpreventable risks to participants of encountering friends or associates at the research laboratory study visits. These are acknowledged and will be reduced as much as possible.

2.3.2 KNOWN POTENTIAL BENEFITS

The potential benefit of this intervention is to decrease alcohol consumption during medication-assisted therapy. This benefit may occur by participating in the trial and the data collected may extend this benefit to future users of the technology. The application is expected to improve their self-awareness and understanding of their current alcohol use, cravings as related to their personal goals, and progress towards recovery goals.

2.3.3 ASSESSMENT OF POTENTIAL RISKS AND BENEFITS

There is a small risk that information provided by a study participant will be seen by someone who is not supposed to see it. We will lower this risk by giving all the information provided by participants a unique identification number instead of their names. Participants are encouraged to discuss any distressing issues that may appear due to their participation in the study. If any identifiable information is released by accident, affected participants will be informed by the PI, apologies for the situation, and notified of steps the study team is taking to rectify the situation as best as possible.

Questions about the participant's habits and history may make them feel uncomfortable. There may be discomfort, social stigmatization, or embarrassment related to giving a urine sample or being seen at the research lab. Our research team will take the utmost caution to avoid creating distress, stigmatization, offending, or degrading participants and their families.

We anticipate that the intervention will lower the average alcohol levels, reduce the number of days of any drinking or heavy drinking during treatment, and decrease the number of days of drinking during the study.

3 OBJECTIVES AND ENDPOINTS

Primary Objective:

To develop and combine mobile technology, geospatial mapping, and biomarker measurement, with individual goal setting and EMA feedback to launch behavioral modification strategies and progress monitoring.

Secondary Objectives:

To develop and consumer-test the mobile application component to help the patient alcohol-related treatment goals at home.

Primary Endpoint:

Biochemically confirmed alcohol abstinence measured thrice daily throughout the 8-week study.

Secondary Endpoints:

The secondary endpoint will include self-reported alcohol use measured by the Timeline Follow Back to assess the frequency and amount of daily drinking via multi-modal EMA data collection.

4 STUDY DESIGN

4.1 OVERALL DESIGN

This pilot study will utilize an A-B-A, completely within-subject design with the intent of recruiting twenty (n=20) total participants. During the first A phase, participants will receive reinforcement for simply submitting breath samples three times per day between 4 and 6 hours apart. In this application, we will utilize a Bluetooth enabled breathalyzer developed by BACtrack, but our smartphone-based technological solution will interact with any alcohol monitoring device, such as BACtrack Skyn. During the B phase, the delivery of reinforcers will be contingent upon the submission of an alcohol negative breath sample on an escalating schedule. The second A phase (i.e., return to the baseline phase) will involve the delivery of reinforcers for simply submitting a sample during the designated windows of time. We will also collect EMA data on stress, anxiety, depression, and other brief measures daily through their smartphone. Each phase will last a total of four weeks (i.e., two weeks of the first A phase, four weeks of the B phase, and then two more weeks of the A-phase) each for a total of 8 weeks of participation. To the extent possible, we will use existing protocols, procedures, and equipment that we have used in previous A-B-A studies.

This study will take place in Greater Inland Northwest area in cooperation with the Community Health Association of Spokane (CHAS) and other outpatient entities, community recruitment, etc. under the auspices of the WSU Program of Excellence in Addictions Research and the Analytics and PsychoPharmacology (APPL).

We will recruit n=20 patients throughout Greater Inland Northwest area. We anticipate a five-month recruitment period, necessitating four recruited per month which is far below our normal recruitment rates. Flyers will advertise the study, and staff and providers will be aware of the study and will be asked to refer potentially interested participants to our investigation. Initial eligibility for a referral will be provided by AUDIT screen and Screen, Brief Intervention, and Referral to Treatment performed at the different treatment centers. Once the treatment center has completed its screening and intervention, they will utilize the AUDIT score to determine the patients that will be provided, the study Research Coordinator contact number for study screening. After an initial phone screening, eligible participants will be scheduled for an in-person study interview, during which they will provide informed consent and complete baseline data collection. During this time, participants will also receive a brief tutorial on how to use the BACtrack breathalyzer and how it integrates with the application on their smartphone. Participants who do not have a compatible iOS smartphone will be provided one for this study. The phones will be supplied from a testing inventory maintained by Managed Health Connections. Participant set-up instructions will also describe the time window for reporting, the definition of zones of use, and will be provided contact information for technical support to be used during the study.

During the A-B-A phase (2-4-2 weeks), participants will be asked to submit three breath samples daily for 8 weeks. They will also be asked to fill out a weekly timeline follow back for alcohol, tobacco, and cannabis use during that period. At the end of the 8 weeks participation period, participants will bring back the phone and fill out the exit questionnaire.

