5.5 STRATEGIES FOR RECRUITMENT AND RETENTION

We anticipate a 5-month recruitment period, necessitating n=4 recruited per month which is far below our normal recruitment rates. Flyers will advertise the study, and staff and providers will be aware of the study and will be asked to refer potentially interested participants to our investigation. As noted elsewhere, while

we will partner with clinics we will also recruit from the community. After an initial phone screening, those deemed eligible will be scheduled for an in-person study interview, during which they will provide informed consent and complete baseline data collection. During this time, participants will also receive a brief tutorial on how to use the BACtrack breathalyzer and how it integrates with the application on their smartphone. Participants who do not have a compatible iPhone Operating System (iOS) smartphone will be provided one for this study. The phones will be supplied from a testing inventory maintained by Managed Health Connections.

Participant set-up instructions will also describe the time window for reporting the definition of zones of use and will be provided contact information for technical support to be used during the study. During the baseline visit participants will receive a \$30 gift cards for their time.

During the first A phase, participants will receive \$2 per sample (regardless of being positive or negative for breath alcohol) submitted instantly, for a maximum payout of \$6 per day.

During the B phase, participants will begin by receiving \$2 per alcohol negative breath sample submitted, escalating by \$0.25 per alcohol negative breath sample submission until a maximum value of \$3.50 per sample is reached. Once this value is reached based on negative breath sample submissions, participants will continue to receive \$3.50 per alcohol-negative breath sample submission. If a participant submits an alcohol positive breath sample, they will be reset to \$2.00 per sample and will need to work up to receive \$3.50 per sample again. Final onetime payment of \$50 will be provided to participants upon return of study devices. Participants will receive electronic payment through a gift card. Payments will be loaded onto the card weekly.

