9.3 STATISTICAL ANALYSES

9.3.1 GENERAL APPROACH

Raw data will be entered directly into the Research Electronic Data Capture (REDCap) system on a secure server by research staff at baseline and all subsequent data from participants via cell phone will flow directly into REDCap.

First, we will perform generalized estimating equations for the repeated binary outcome of alcohol abstinence. This model will include the variables of 1) Time (individually varying timestamp from when the breath sample was submitted) and 2) Phase (A, B, A).

Second, we will analyze the outcome of 1) self-reported heavy drinking days (4+ standard drinks per drinking day for women, 5+ standard drinks per drinking day for men), 2) self-reported craving, and 3) self-reported craving, all over time.

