9.3.2 ANALYSIS OF THE PRIMARY ENDPOINT(S)

Our primary outcome is biochemically confirmed alcohol abstinence, measured thrice daily throughout the 8-week study. Age and risky drinking will be determined based on self-report at the screening interview. Risky drinking will be defined using the AUDIT and AUD diagnosis will be confirmed by administering the DSM-5 checklist.²⁷ Research staff will also use this interview to assess for possible exclusionary cognitive or psychotic disorders using the MINI Neuropsychiatric Interview (M.I.N.I.). This variable will be analyzed as a repeated dichotomous variable.

If data are missing, missingness will be handled in a manner consistent with current expert recommendations, some of which have been established by our own team.^{20,22,24,38-43} Our approach emphasizes 1) either maximum likelihood or multiple imputations, and 2) extensive sensitivity analyses, including missing not at random approaches, to examine the robustness of treatment effects across varying assumptions. Maximum likelihood and multiple imputations have both shown exceptional performance compared to other, more common methods of handling missing data when the assumption of "missing at random" can be safely satisfied.³⁹

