9.3.3 ANALYSIS OF THE SECONDARY ENDPOINT(S)

Secondary outcomes will include mobile usage, EMA bout completions, and self-reported alcohol use measured by the Timeline Follow Back²⁸ to assess the frequency and amount of daily drinking via multimodal EMA data collection by time, date and location. The Addiction Severity Index and quality of life in several domains (e.g., psychiatric, legal, medical) will be assessed at baseline.

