9.3.5 BASELINE DESCRIPTIVE STATISTICS

We will initially run descriptive statistics across baseline variables to characterize the sample. All inferential results will be presented as point estimates with 95% confidence intervals, and we will use an alpha error rate of 0.05 as the threshold for statistical significance. Our approach is consistent with that of several similar RCTs involving tobacco smoking and alcohol use disorders.^{12,13,24,34-37}

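### Each momentary breath reading is analysed as alcohol abstinence, so the A-B-A pattern alone cannot separate less drinking from re-timed drinking, and the self-report that could check this has three conflicting schedules

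*Protocol*

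**What the plan says.** **Endpoint and model.** Section 3 defines the primary endpoint as "Biochemically confirmed alcohol abstinence measured thrice daily throughout the 8-week study". Section 9.3.1 plans "generalized estimating equations for the repeated binary outcome of alcohol abstinence", with phase and the time stamp of each breath sample as model terms. Section 9.3.2 adds: "This variable will be analyzed as a repeated dichotomous variable". The unit of analysis is thus the single reading. No section turns readings into an abstinent day or period. Section 9.3.5 states that "we will use an alpha error rate of 0.05 as the threshold for statistical significance".

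**Sampling.** Section 4.1, describing the first A phase, says "participants will receive reinforcement for simply submitting breath samples three times per day between 4 and 6 hours apart". It then asks for three samples daily for all 8 weeks. Section 8.2 gives a 30-minute window after each prompt. Prompts draw on a profile that holds reporting times, and also on prior reporting.

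**Payment.** In the first A phase each sample earns 2.00 USD "regardless of being positive or negative for breath alcohol" (Section 5.5). The second A phase again pays for submission (Section 4.1). In B only a negative sample is paid, rising by 0.25 USD from 2.00 to 3.50 USD, with a reset to 2.00 USD after a positive one.

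**Self-report.** Section 9.3.1 plans an analysis of "self-reported heavy drinking days" over time, and Section 3 makes the Timeline Follow Back the secondary endpoint. For weeks 1 to 8 that instrument is scheduled three times daily in Table 1 (Section 1.2), weekly in the text of Section 4.1, and not at all in Table 2 (Section 8.1), where the cell is empty.

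**The concern.** A negative breath reading shows that no alcohol was detected at that moment. Calling it confirmed abstinence claims more, because much of each day lies outside the sampled span. This matters in an A-B-A design because the financial reason to keep alcohol out of the windows switches on in B and off again in the second A phase. Re-timing alone would then move the phase term in the same direction, and with the same reversal, as a true reduction in drinking. Return to baseline is the design's usual safeguard, but it does not separate these two explanations.

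Daily self-reported drinking is the natural cross-check, since it covers the hours between samples. If staff followed Table 2, the secondary drinking outcome would not be collected after baseline. The check would be lost, along with a stated secondary endpoint.

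**Working it through.** **1. Payment schedule, to confirm that only B depends on the result.** Inputs are from Section 5.5 and the 2-4-2 week phases of Section 4.1.
- Each A phase: 14 days x 3 x 2.00 = 84.00 USD; two phases = 168.00 USD.
- B phase, all 84 samples negative: 2.00 + 2.25 + 2.50 + 2.75 + 3.00 + 3.25 = 15.75; plus 78 x 3.50 = 273.00; total 288.75 USD.
- Baseline 30 + 168.00 + 288.75 + final payment 50 = 536.75 USD.

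This is exactly the maximum in the phone screening script (Section 12), so the reading of the payment rules is right.

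**2. Longest daily gap.** The span from first to last sample is 2 x 4 = 8 h to 2 x 6 = 12 h. The gap to the next day's first sample is 24 - 12 = 12 h to 24 - 8 = 16 h.

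**3. What a positive last sample costs in B.** This assumes the same weekdays in each of the 4 weeks, with the range taken over all choices of weekday and a reset after each positive.
- 2 days a week: 54.75 to 69.75 USD lost.
- 5 days a week: 129.75 to 139.25 USD lost.
- Every day: (2.00 + 2.25) x 28 = 119.00 USD paid, so 288.75 - 119.00 = 169.75 USD lost.

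In either A phase the same readings cost nothing.

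**4. Illustration of a spurious phase effect.** The displacement figures are assumptions; the protocol gives none. Let d be the share of drinking days, unchanged across phases; p the chance that a drinking day yields one positive of three samples in A; and f the share of those positives moved out of the windows in B. The negative share is 1 - dp/3 in A and 1 - dp(1 - f)/3 in B. With p = 1:

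| d | Negative in A | B, f = 0.25 | Gain (points); OR | B, f = 0.5 | Gain (points); OR |
|---|---|---|---|---|---|
| 5/30 = 0.167 | 0.944 | 0.958 | 1.4; 1.35 | 0.972 | 2.8; 2.06 |
| 0.3 | 0.900 | 0.925 | 2.5; 1.37 | 0.950 | 5.0; 2.11 |
| 0.5 | 0.833 | 0.875 | 4.2; 1.40 | 0.917 | 8.3; 2.20 |
| 0.7 | 0.767 | 0.825 | 5.8; 1.43 | 0.883 | 11.7; 2.30 |

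The first row uses the screening floor in Section 12, where fewer than 5 drinking occasions a month is ineligible, taking each as a separate day in 30. With f = 0 the gain is 0 and the odds ratio is 1.0. With p = 0.1 and f = 0.5 the gain is 0.5 points at d = 0.3 (0.990 to 0.995) and 1.2 at d = 0.7 (0.977 to 0.988). As positives become rare the odds ratio approaches 1/(1 - f), so it largely restates the assumed f; the point differences are more informative.

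**5. Self-report schedules for weeks 1 to 8.**

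| Place | Timeline Follow Back | Daily drinking in all phases? |
|---|---|---|
| Section 1.2, Table 1 | three times daily | yes |
| Section 4.1, text | weekly, on the day-by-day calendar form in Section 12 | yes |
| Section 8.1, Table 2 | empty cell | no |

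Neighbouring rows of Table 2 keep their weeks 1 to 8 entries, so a lost cell is unlikely. Even without that row, three times daily and weekly disagree.

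**The case against.** **The endpoint states its own resolution.** It is a repeated binary reading taken thrice daily, and drinking days are a separate self-reported outcome. That is fair: nothing in the protocol converts readings into continuous abstinence. The label still claims more than the reading shows, and the label is what a conclusion would carry.

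**Payment by result only in B is the intervention.** This stands. The contingency is not a defect. The point is only that it also changes the reason to time drinking.

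**Re-timing may be slight.** This also stands. The 12 to 16 hours include sleep, and unsampled is not the same as undetectable: the next morning's sample may catch heavy or late drinking. If drinking in A already falls mainly after the last sample, little is left to displace. Prompts are not shown to fall at fixed times, although the set-up instructions describe the reporting window, so some foreseeability remains.

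**The check is not lost under every schedule.** A reader might infer from three conflicting entries that no usable self-report exists. The protocol does not support that, since two of the three schedules would supply it.

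**Time of drinking.** A reader might also infer that the day-by-day calendar form cannot support an analysis by time. Section 9.3.3 plans "the frequency and amount of daily drinking via multimodal EMA data collection by time, date and location", which ties time and location to the momentary assessments rather than to that form. No criticism is made on this ground.

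**It is a proof of concept.** Section 9.1 says so, and this tempers the stakes. Section 9.3.5 nevertheless plans inferential results.

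**Conclusion.** The point holds in a limited form. The protocol establishes three things: single readings are modelled as abstinence, the longest daily gap is 12 to 16 hours, and only B pays by result. It follows that a rise in B with reversal in the second A phase is not, on its own, proof of less drinking. The conflicting Timeline Follow Back schedules are a plain error and need correcting whatever view is taken of re-timing.

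A reader might go further and infer that the phase effect will be largely spurious, with an odds ratio near 2. The documents do not support that: no displaced share is given anywhere, and the figures in the working only illustrate assumed shares. Across those assumptions the gain runs from nothing to about 12 points, and near the screening floor it is 1.4 to 2.8. This merits a change to the protocol, with medium confidence about its practical effect.

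**What to change.** 1. Reconcile the Timeline Follow Back entry across Table 1, Section 4.1 and Table 2 so that daily self-reported drinking is collected in all three phases.
2. Name the primary endpoint an alcohol-negative breath sample, the term the payment rules already use, and limit the conclusion to it. At the same time reconcile what counts as negative: Sections 4.1 and 5.5 pay for alcohol-negative samples, while the phone screening script describes payment for readings below a BAC of 0.08.
3. Add one supportive table by phase, giving the share of self-reported drinking days on which all three scheduled samples were submitted and negative. Show days with a missing sample separately, because Section 5.5 states a reset only for a positive sample and skipping is a rival explanation. Put self-reported drinking days and drinks per drinking day beside it, since the share can also rise if people truly drink less per day. State in the conclusion whether self-report agrees with the breath result.

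The cost is endpoint wording, one schedule row, one cut-off and one table, with no new visits or devices. Participant burden depends on which Timeline Follow Back schedule is kept. The drawbacks are partial reliance on unblinded self-report and a possibly less favourable conclusion.
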